4.4 Handling of measurements obtained for early withdrawals

Participants who withdraw early from the study for any reason will be asked to return to the clinic to complete the SFU visit. The SFU procedures performed at this visit are as shown in the Schedule of Activities for Part B in the protocol and will be summarized together with all other SFU visit data in the tables.

4.5 Interim analyses and data monitoring

No formal interim analyses are planned during Part B of this study.

A SSC will be implemented prior to the start of Part B. In consultation with the SMC, the SSC will recommend to the Sponsor the dose and dosing regimen to be taken forward for Part B. The SSC members will include the coordinating investigator, supporting co-investigators, and clinical experts not involved in the study. The medical, scientific, and clinical study expertise of the SSC will assist the Sponsor in identifying and resolving any study related issues, such as study design, study implementation and conduct, and data analysis and reporting.

The SMC already established for Part A of the study, comprising investigators from UK sites participating in Part A and key Sponsor personnel, will continue as the SMC for Part B as long as they are actively enrolling study participants into the study. In addition, investigators from US sites who are actively enrolling study participants into Part B of the study will also become members of the SMC for Part B.

Responsibilities of the SMC for Part B include:

- Review of safety data for study participants including review and provision of adjudication of individual DLTs, if needed;
- Review of available PK and PD biomarker data;
- Make dose escalation recommendations;
- Determination of the MTD, if applicable.

The SMC will convene after the last participant in a given cohort has completed the required 28-day DLT Observation Period. The SMC will decide whether to halt dose escalation, further expand the dose level to gain additional safety data, or determine the next dose level to be tested.

All data presented to the SMC will be cumulative in order that the members can review and discuss the data in its totality at the end of all completed cohorts, i.e. all safety information beyond Cycle 1 for all previous cohorts will be presented cumulatively for review during each subsequent SMC meeting.

In addition to the planned SMC data review meetings, the Sponsor and the SMC will have the ability to hold/request *ad hoc* meetings should they be deemed necessary (e.g. if safety concerns arise during Part B of the study and/or during other ongoing nonclinical and clinical studies).

4.6 Multicenter studies

Part B of this study is planned to be conducted at study sites in the UK and US. With the exception of participant disposition, no summaries will be presented by site.

4.7 Multiple comparisons/multiplicity

Not applicable.

4.8 Use of an efficacy subset of participants

The PPS will be used as the primary analysis set for the summaries of the exploratory antitumor activity endpoints in Part B.

4.9 Active-control studies intended to show equivalence

Not applicable.

4.10 Examination of subgroups

Not applicable.

5. STUDY POPULATION CHARACTERISTICS

5.1 Study participant disposition

The number of study participants who were screened for Part B of this study, the number and percentage of screen failures and the primary reasons for screen failure will be summarized for the ES. A listing of participants who did not meet the eligibility criteria for Part B will also be presented for the ES. In addition, the disposition of study participants screened and who received study treatment will be summarized by country and site. This table will include, for each site and overall, site number, principal investigator name, the dates of the first participant in and the last participant out, the number of participants screened (ES), the number of screen failures, the number of participants who were treated (SS) and included in the PPS, PKS, ADAS and PDS. Disposition in each analysis set across all study sites will be summarized by treatment group.

The number of study participants who received study treatment and the primary reason for discontinuation of UCB6114 and TFD/TPI study treatment during Part B will be summarized by treatment group, together with the number and percentage of participants who continued participation in the study after discontinuation of study treatment (at subsequent scheduled visits and/or SFU visit and Final Visit). This summary will be based on the SS.

The number of study participants enrolled into Part B, who were screen failures as well as the number of eligible participants who were not treated will be presented for the ES. For those participants who did not receive study treatment, the reasons for early discontinuation from the study will be summarized.

Of those participants who received UCB6114, the number and percentage of participants who completed the study (i.e. participants who received at least 2 complete cycles of UCB6114 and attended the SFU visit), who received at least 2 complete cycles of UCB6114 but who did not attend the SFU visit and who discontinued early from Part B, together with the primary reasons for study discontinuation will be presented for all participants.

The number and percentage of participants who discontinued due to AEs will be summarized separately for all participants, based on the SS. This will be used for European Union Drug Regulating Authorities Clinical Trials (EudraCT) reporting.

The following study disposition tables will also be presented by gastric adenocarcinoma, adenocarcinoma of the gastroesophageal junction (Gastric/GEJ-Cancer) and colorectal

adenocarcinoma (CRC) tumor type depending on the number of participants with specific tumor types.

- Disposition and Reasons for Discontinuation of Study Treatment;
- Disposition and Study Discontinuation Reasons;
- Discontinuation of the Study Due to AEs.

Visits impacted by COVID-19 will be listed for the ES. This listing will include, visit, visit date, relative day, impact category (e.g. visit performed out of window, visit performed by telephone, visit not done, missed study drug administration/dispensation, termination of study participation), relationship to COVID-19 (confirmed COVID-19 infection, suspected COVID-19 infection, general circumstances around COVID-19 or other) and a narrative for the event. The number and percentage of participants with visits impacted by COVID-19 will be presented by treatment group and by impact category. This summary will be presented for the different relationships to COVID-19. The denominator for the percentage calculations will be the number of participants in the SS.

In addition, the following listings will be presented:

- Study participant disposition (ES);
- Study treatment discontinuation (SS);
- Study discontinuation (ES);
- Visit dates (ES);
- Participant analysis sets and exclusions from analysis sets (ES)*.

*DES is not included in this listing as it is only relevant for the SMC, and not required for the CSR.

The listing of study participant disposition will include the date of informed consent, date and time of first and last dose of study treatments (UCB6114 and TFD/TPI), date of early study discontinuation (if applicable) and primary reason for discontinuation.

Separate listings of UCB6114 and TFD/TPI study treatment discontinuation will include date and time of first and last dose of study treatments, date of decision to discontinue study treatment and primary reason for discontinuation of study treatments, date of clinical progression (if applicable), number of doses of study treatments received (based on 2 doses per cycle for UCB6114), total dose of study treatment received across all cycles, number of complete cycles of study treatment received, and whether or not the participant had continued participation in the study (at subsequent visits, the SFU visit or the Final Visit).

Note that a participant is deemed to have completed a full cycle of study treatment if they received the planned dose of UCB6114 on Days 1 and 15 of the cycle (i.e. the infusion was not permanently discontinued due to an AE or other reason such that less than the planned dose was received) and a decision was not made to discontinue UCB6114 up to and including Day 28 relative to Day 1 of the cycle. This will be derived based on a participant's last dose of UCB6114 and whether or not the participant attended the visit at which they were scheduled to receive their next dose of UCB6114. For example, if a participant received UCB6114 on Day 1 and Day 15 of

Cycle 1 and attended the clinic for their UCB6114 infusion on Day 1 of Cycle 2 then the participant will be counted as having completed Cycle 1. If the participant did not attend Day 1 of a subsequent cycle, then it is likely that a decision was made to discontinue their UCB6114 treatment and/or the study. Therefore, the date that the decision was made to discontinue UCB6114 will be used to determine whether the participant completed a cycle of study treatment. If a decision was made to discontinue UCB6114 on >Day 28 relative to Day 1 of the particular cycle then the participant will be counted as having completed the cycle. For any interim deliveries at a data cut-off, if the participant did not attend Day 1 of their next cycle and there was no decision to discontinue UCB6114, then the latest date available for that participant should be used to determine whether they have completed a 28-day cycle.

Whether or not a participant has completed the study is defined as having received at least 2 complete cycles of UCB6114 and attended the SFU visit. The investigator will record a study participant's disposition status at study termination according to this definition of a 'completed' participant, however, a study completion flag will also be programmatically derived based on the relevant data on the database and the above rules for defining completion of a full cycle of UCB6114.

The listing of study discontinuation will include the primary reason for early study discontinuation, the number of cycles of UCB6114 received, and the total number of days on UCB6114.

5.2 Protocol deviations

Important protocol deviations will be identified and classified by the deviation types defined in the IPD specification document, as per [Section 3.4](#).

A listing of all IPDs identified at the DEM will be presented for all study participants based on the SS and will include the deviation type and description. In addition, a listing of all protocol deviations related to COVID-19 (whether considered important or not) will be presented for the SS. The number and percentage of participants in the SS with IPDs will be summarized by treatment group and for all participants for each deviation type. The number and percentage of participants who were excluded from the PPS will also be presented. The denominator for the percentage calculations will be the number of participants in the SS. A summary will also be presented for all protocol deviations related to COVID-19, all IPDs related to COVID-19 and all IPDs related to COVID-19 leading to exclusion from the PPS.

6. DEMOGRAPHICS AND OTHER BASELINE CHARACTERISTICS

6.1 Demographics

A by-participant listing of demographics will be presented based on the ES. This will include the year of birth, age (as entered by investigator in the eCRF in years), sex, race, ethnicity, height (in cm), weight (in kg) and body mass index (BMI, in kg/m²). Height will be the measurement obtained at the Screening visit and weight will be the last non-missing value prior to the first dose of UCB6114.

The BMI will be derived in the database using the height and weight measurements recorded at the Screening visit and will be automatically reported to 1 decimal place on the eCRF.

All demographic characteristics (except for date of birth) will be summarized by treatment group and for all study participants based on the SS. The summary of age will include descriptive statistics and categorical summaries, the latter based on requirements for EudraCT and clinicaltrials.gov reporting. In addition, the summary of demographic characteristics will be presented by Gastric/GEJ-Cancer and CRC tumor type depending on the number of participants with each specific tumor type.

For the EudraCT reporting, the categories will include:

- 18 to <65 years;
- 65 to <85 years.

For clinicaltrials.gov reporting, the categories will include:

- \leq 18 years;
- 19 to <65 years;
- \geq 65 years.

Childbearing potential and method of birth control will be listed for the ES.

6.2 Cancer history

All cancer history data for Part B participants will be listed for the ES. This listing will include date of initial diagnosis, tumor type, TNM Classification of Malignant Tumors (TNM) classifications and stage, Duke's score (participants with colorectal adenocarcinoma only), histological and cytological diagnosis details (as relevant), whether the participant had any metastases and associated anatomical location, and whether the participant had received any prior anti-cancer therapies (including the number of lines of any prior systemic therapies, prior radiation therapies and prior anti-cancer surgeries).

Time since initial diagnosis (calculated in months using date of Screening visit and date of initial diagnosis and multiplying the duration in days by 12/365.25), tumor type, T, N, and M classifications and TNM stage, Duke's score (participants with colorectal adenocarcinoma only), presence of metastases and anatomical location of metastases will be summarized by treatment group and for all study participants based on the SS. In the summaries of categorical variables, percentages will be calculated based on the number of study participants with non-missing data. Further, for the Duke's score, the denominator for the percentage calculation will be the number of study participants with colorectal adenocarcinoma.

Cancer history will be presented by Gastric/GEJ-Cancer and CRC tumor type depending on the number of participants with specific tumor types.

6.3 Prior anti-cancer therapy

Details recorded for each line of prior anti-cancer systemic therapy received by a study participant will be listed for the ES. This listing will include the line and type of systemic therapy, intent, drug name and dose, formulation, indication (current/ultimate), start and end dates, number of cycles received and the number of days per cycle, the participant's best

response and the date of that best response, reason for discontinuation and whether the participant had disease progression prior to the next line of systemic therapy. If there was progression, then the date of progression will also be listed. In addition, time from completion of the last prior anti-cancer systemic therapy to the start of UCB6114, whether the participant had progression after the last line of systemic therapy and, if so, the time from progression to the start of UCB6114 will be derived and listed.

For those participants in the ES who received prior radiotherapy, the following data will be listed: treatment site, type of radiotherapy, intent, settings (concurrent with other anti-cancer systemic therapy or stand-alone radiation therapy), and, if concurrent radiotherapy, the anti-cancer systemic therapy line that the radiotherapy was given with and the drug name. In addition, the start and stop dates, total cumulative dose (if known), number of fractions (if known), the participant's best response to radiotherapy and whether the tumor at the treatment site had progressed since radiotherapy will be included in this listing.

A further listing of prior anti-cancer radiotherapy with systemic therapy regimens will be presented for participants in the ES who had concurrent prior systemic therapy and radiotherapy as their prior anti-cancer therapy. This listing will include the relevant data described above together with the participant's best response to that regimen.

Date of surgery/procedure, anatomical location, description of the surgical procedure and whether the tumor was completely removed will be listed for those study participants in the ES who had prior anti-cancer surgeries or procedures.

The following summaries of prior anti-cancer therapy regimens and surgeries will be presented by treatment group and for all participants for the SS:

- Number of prior anti-cancer therapy regimens (0, 1, 2, 3, >3) (including all anti-cancer systemic therapy lines given alone and concurrently with radiotherapy)
- Best response to the most recent prior anti-cancer therapy regimen
- Number of prior anti-cancer systemic therapy + radiotherapy regimens (0, 1, 2, 3, >3)
- Best response to the most recent anti-cancer systemic therapy + radiotherapy regimen
- Reasons for discontinuation of the most recent line^[a]
- Time from completion of most recent line^[a] to the start of UCB6114 (<1 month, 1-<3 months, 3-6 months, >6 months)^[b]
- For participants that progressed after their most recent line^[a], the time from progression to the start of UCB6114 (<1 month, 1-<3 months, 3-6 months, >6 months)^[b]
- Number of prior anti-cancer radiotherapies (including radiotherapies given alone and concurrently with anti-cancer systemic therapy) (0, 1, 2, >2)
- Number of prior anti-cancer surgeries and procedures (0, 1, 2, >2)

^[a] Most recent line is the last prior anti-cancer therapy regimen received which may be a prior anti-cancer systemic therapy given alone or concurrently with radiotherapy.

^[b] 1 month = 30 days.

Time from completion and time from progression relative to the last line of anti-cancer systemic therapy will also be summarized using frequency counts and percentages as well as summary statistics.

The number and percentage of participants with any prior anti-cancer systemic therapy, and any prior anti-cancer systemic therapy given concurrently with radiotherapy will be summarized for the SS by treatment group and for all participants, and by WHODD Anatomical Main Group [Level 1 term text], Pharmacological Subgroup [Level 3 term text] and PT.

Prior anti-cancer therapy will be presented by Gastric/GEJ-Cancer and CRC tumor type depending on the number of participants with specific tumor types.

6.4 Cancer status at Screening

The current cancer status of study participants at entry into Part B of this study will be assessed at the Screening visit and listed for the ES. This listing will include tumor type, T, N and M classifications and TNM stage and Duke's score (participants with colorectal adenocarcinoma only), histological and cytological diagnosis details (as relevant), whether the participant has any metastases and associated anatomical location, whether the tumor is recurrent and whether the participant had relapsed from their last line of anti-cancer therapy.

Tumor type, T, N and M classifications and TNM stage, Duke's score (participants with colorectal adenocarcinoma only), presence of metastases and anatomical location of metastases, and time since relapse on last line of therapy (calculated in days using the date of the Screening visit and date of relapse) will be summarized by treatment group and for all study participants based on the SS. In the summaries of categorical variables, percentages will be calculated based on the number of study participants with non-missing data. Further, for Duke's score, the denominator for the percentage calculation will be the number of study participants with colorectal adenocarcinoma.

Cancer status will be presented by Gastric/GEJ-Cancer and CRC tumor type depending on the number of participants with specific tumor types.

6.5 Medical history and concomitant diseases

Medical history will be listed for the ES and summarized by MedDRA® system organ class (SOC) and preferred term (PT) by treatment group and for all study participants for the SS. The reported term will be included in the listing. Previous medical history (any previous medical conditions with a stop date prior to the start of UCB6114) and ongoing medical history (any ongoing medical conditions with a missing stop date but recorded as ongoing on the eCRF) will be summarized separately. These summaries will include the number and percentage of study participants and will be sorted alphabetically by SOC and by descending incidence of PT within each SOC, based on the incidence in all study participants.

Non-anti-cancer procedure history will be listed for the ES and concomitant medical procedures performed during the study will be listed for the SS.

Medical history and concomitant disease will be presented by Gastric/GEJ-Cancer and CRC tumor type depending on the number of participants with specific tumor types.

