4.2 Handling of dropouts or missing data

There will be no imputation of missing data unless otherwise stated in the sections below.

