6.6 Prior and concomitant medications

Prior medications will include any medications that started prior to the date of the first dose of UCB6114. This will include medications that started prior to the first dose of UCB6114 and continued after.

Concomitant medications will include medications with a start date on or after the first dose of UCB6114 and prior to the date of the last dose of UCB6114 + 30 days, and whose stop date is either missing, or on or after the date of the first dose of UCB6114. Any medications with a start date prior to the first dose of UCB6114 and a stop date after, or continued to be ongoing during the study, will also be classified as concomitant medications. Medications with a start date > 30 days after the last dose of UCB6114 will be considered as post-study medications and will not be included in the summaries of concomitant medication.

Any medication that started prior to, and stopped after the first dose of UCB6114 or continued to be ongoing during the study, will be classified as both prior and concomitant.

Any medications with missing start dates will be classified as both prior and concomitant.

Any medications with partially missing dates will be handled as described in [Section 4.2.3](#) to classify them as prior or concomitant provided that a stop date is not present or a stop date is present but prior to the first dose of UCB6114.

All medications (prior, concomitant and post-study) will be listed for the ES. Any prohibited concomitant medications, rescue medications or steroid use will be identified via a medical review and flagged in this listing.

Prior and concomitant medications (per the definitions above) will be summarized for the SS by treatment group and by WHODD Anatomical Main Group [Level 1 term text], Pharmacological Subgroup [Level 3 term text] and PT. The reported term will be included in the listing. Separate summaries will be presented for prior medications and concomitant medications. As per the definitions above, prior medications which continued into the Treatment Period will also be classified as concomitant and will be included in both summaries.

All tabulations will be sorted alphabetically by Level 1 term, alphabetical Level 3 term within Level 1 and decreasing frequency of PT in all study participants.

A glossary of all prior and concomitant medications will be presented for the SS including the Anatomical Main Group (Level 1), Pharmacological Subgroup (Level 3), PT and reported term.

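### A medical condition present at first dose with a recorded stop date on or after that dose fits neither the previous nor the ongoing definition, so both medical history summaries omit it

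*SAP*

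**What the plan says.** The SAP document contains one plan for Part B and one for Part C, and Section 6.5 (Medical history and concomitant diseases) is worded the same way in both on this point. It opens with the general provision: "Medical history will be listed for the ES and summarized by MedDRA® system organ class (SOC) and preferred term (PT) by treatment group", the summary being for the Safety Analysis Set. It then splits the history into two categories that are to be summarized separately:

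- Previous: "any previous medical conditions with a stop date prior to the start of UCB6114".
- Ongoing: "any ongoing medical conditions with a missing stop date but recorded as ongoing on the eCRF".

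No third category or catch-all follows.

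Section 6.6 (Prior and concomitant medications) deals with the same timing for drugs. It counts as concomitant "Any medications with a start date prior to the first dose of UCB6114 and a stop date after", and it adds that a medication spanning the first dose is both prior and concomitant.

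On missing data, Section 4.2 says: "There will be no imputation of missing data unless otherwise stated in the sections below". Section 4.2.3 then lists the purposes for which partial dates may be imputed: adverse events, medications, and intervals in the cancer history. Classifying medical history is not among them.

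**The concern.** The two definitions use different reference points. Previous is fixed to a date, the start of UCB6114. Ongoing is fixed to the state of the eCRF record when the data are extracted. Two categories defined in this way need not cover every record, and here they do not.

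The record that falls between them is one the section's own title suggests it should show: a disease the participant had when treatment began. Under Section 6.6, a drug given for that disease and stopped after first dose would be tabulated as concomitant, while the disease itself would be missing from both history summaries.

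There is also a question of stability. The introduction to each plan says that there may be several data cut-offs before the final lock. If a stop date is entered between two cut-offs, the condition moves from the ongoing summary to neither summary, although nothing about the participant at first dose has changed. A baseline summary should not depend on when it is run.

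**Working it through.** The SAP gives no figure to reproduce here. The check is to take each possible state of the stop date and compare it with the two definitions in Section 6.5.

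1. **Stop date before the start of UCB6114.** Meets the previous definition. Result: previous.
2. **Stop date missing, recorded as ongoing.** Meets the ongoing definition. Result: ongoing.
3. **Stop date present, on or after the start of UCB6114.** The date is not before the start, so the condition is not previous. The date is not missing, so it is not ongoing. Result: neither.
4. **Stop date missing, not recorded as ongoing.** There is no date to place before the start, and no ongoing entry. Result: neither.

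State 3 is the subject of this point. State 4 is a data-quality case that the same edit could settle.

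Next, does another section close state 3?

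- Section 4.2 rules out imputation unless stated, and the purposes in Section 4.2.3 do not cover medical history. In any case the date in state 3 is known, so imputation would not help.
- Section 6.6 has the missing rule, but for medications only.
- The opening sentence of Section 6.5 keeps the record in the Enrolled Set listing. It does not place it in either of the two separate summaries.

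Nothing closes the gap, and the Part C text leads to the same result.

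Finally, what depends on these tables? Section 8.2 classifies an adverse event as treatment-emergent from its own start date relative to UCB6114, or from a worsening that is entered as a new event. Section 8.2 takes the DLT flag from the investigator's entry on the eCRF. Section 3.5.7 bases escalation decisions on the DLT Evaluable Set. None of these uses the medical history summary.

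**The case against.** The strongest reply is that the case may never arise. It needs a site to return to a history entry and add a stop date on or after first dose. If history is recorded at Screening and left as ongoing, every such condition stays in the ongoing summary. The SAP does not say whether the form is updated, and the eCRF is not part of the document. This stands: the gap is conditional, and its frequency cannot be stated.

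The same reply weakens the comparison with Section 6.6. Medications come from a log in which on-study stop dates are expected, so that section does not show that history records behave in the same way. It is also not a perfect model, because a drug started earlier and stopped exactly on the first-dose date fits neither of its concomitant sentences. What survives is narrower: the authors saw the need for a rule covering first dose in one section and did not write one in the other.

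It can also be said that nothing is lost from reporting. The listing holds every condition, and with at most 9 evaluable participants per dose level it can be read directly. The opening sentence of Section 6.5 might even be taken to promise an overall summary, although the text is not explicit. The first part stands and limits the loss to the two summaries.

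A reader might infer three stronger things that the document does not support:

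- **That every baseline condition resolving on study is omitted, and more of them as follow-up lengthens.** Both assume routine updating of the history form, which the SAP does not state.
- **That TEAEs are judged against the ongoing table.** Reviewers may read the two together, but no derivation in the SAP does so.
- **That the row percentages measure the damage.** With 3 to 9 participants expected per dose level (Section 2.4), one participant is 1/3 = 33.3% to 1/9 = 11.1% of a column, and 1/27 = 3.7% of a full Part. That is true of any table in the study. The percentage does not even move if the participant has another qualifying record under the same preferred term.

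**Conclusion.** The point holds as a minor error in a stated rule. On the wording of Section 6.5 in both plans, a condition present at first dose with a recorded stop date on or after the start of UCB6114 is left out of both separate medical history summaries. It remains in the Enrolled Set listing.

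The conclusion rests on the literal definitions and on one assumption, that at least some stop dates are entered on the history form after first dose. If none are, the summaries are complete in this respect. The SAP gives no basis for estimating how many records are involved. The consequence is limited to descriptive baseline tables.

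**What to change.** In Section 6.5 of both the Part B and the Part C plan, define ongoing medical history as conditions recorded as ongoing, or with a stop date on or after the first dose of UCB6114. Leave the previous category as it is. States 1 to 3 above then each have one category, set by status at first dose, and a stop date entered between cut-offs no longer removes a condition from the tables.

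While the sentence is open, add one line on the two cases this wording leaves unsettled: a partial stop date that could fall on either side of first dose, and a missing stop date with no ongoing entry.

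The cost is one phrase and one programming condition per plan, with the further line optional. No other analysis changes.
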